#### 4.3. Schemas

#### 4.4. Duration of Study

The duration of the study is anticipated to be approximately 24 months. We anticipate study enrollment will take approximately 20 months, individual patient active participation will last approximately 3 months, and genetic counselor active participation will last approximately 9 months. We expect patient participants to spend approximately 8 hours engaged in study activities

over the approximately 3 months of their enrollment. Hours of patient participation may vary by patient's use of the workbook and particular family situation. We expect genetic counselor participants to spend approximately 4 to 20 hours engaged in study activities over the approximately 9 months of enrollment. Genetic counselor time will vary by the number of patients a genetic counselor has enrolled into the study.

#### 4.5. Intervention Description

The educational workbook is in a PDF format. The workbook contains a series of lessons and exercises on the following topics:

What is Lynch Syndrome?

Why should I tell my family members about Lynch Syndrome?

Who is at risk for Lynch Syndrome and who should I reach out to?

Create a list of first-degree relatives at risk for inheriting Lynch Syndrome

What should I tell my family members about Lynch Syndrome?

Create a script for discussing Lynch Syndrome with family

What are common concerns family members might express?

How should I tell my family members about Lynch Syndrome?

Create a plan to reach out to each family member

Create goals for talking to family members

What if my conversation with family didn't go well?

What are common terms and questions about Lynch Syndrome?

How can I manage having Lynch Syndrome?

Where can I find additional information about living with Lynch Syndrome

#### 4.6. Follow Up

After a genetic counselor has provided the contact information of an interested patients or the patient has directly contacted the research team by email, the UNC research team will reach out to the patient in approximately 1 weeks to gather informed consent and will conduct a follow up interview and survey after approximately 4 weeks.

All interviews will be completed through Zoom using a semi-structured interview guide developed by the research team based on the Consolidated Framework for Implementation Research The interviews will be conducted by the research assistant and a trained interviewer and recorded. The recordings will be transcribed for qualitative template analysis to identify major themes.

During the follow-up session, participants will also complete an electronic survey to assess the following feasibility concepts: acceptability of workbook, self-efficacy, Lynch Syndrome knowledge, Lynch Syndrome perceived knowledge, cost of workbook use.

#### 4.7. Statistical Considerations

##### 4.7.1. Sample Size and Accrual

With up to five genetic counselors across sites or through LSI, we will enroll 15 Lynch Syndrome patients. The study personnel have conducted previous qualitative research on genetic testing for cancer care, including Lynch Syndrome. Thematic saturation in those studies was reached through 15 interviews with patients and providers. Thus, we expect to reach thematic saturation on the feasibility of the workbook for patients in the template analysis process by enrolling approximately 15 patients in the pilot study. Because we are working with a small number of patients for a rare disease, we anticipate working with a small number of genetic counselors. We expect general feasibility feedback from providers on the workbook.

##### 4.7.2. Statistical Analysis Plan Data Analysis Plans

The transcribed qualitative interviews will be double coded using template analysis in NVIVO, a qualitative data analysis tool, by the research assistant and another investigator. Expected themes (practicality, integration, demand, and reach) will be a prior coded in the transcripts, but the themes will be modified, removed, or additional themes will be coded as identified to create a codebook. A final codebook will be created and used to double code all interview transcripts. We will compile the major themes and subthemes identified regarding the workbook feasibility.

During the follow-up session, participants will complete an electronic survey to assess the following feasibility concepts. Acceptability of workbook will be measured through 7 questions for patients rated with a scale 1 (very unacceptable) to 5 (very acceptable). A score of over 80% suggests an acceptable intervention. Self-efficacy in communicating about Lynch Syndrome and the importance of family testing will be measured through 5 questions rated with a scale 1 (very low confidence) to 5 (very high confidence). A score of 15 or higher suggests moderate to high self-efficacy. Lynch Syndrome knowledge will be measured by 7 multiple-choice questions and a score of 4/7 or higher suggests moderate to high knowledge of workbook users. Lynch Syndrome perceived knowledge will be measured by 7 questions rated with a scale 1 (very low confidence) to 5 (very high confidence) and a score of 21 or higher suggests moderate to high perceived knowledge. The cost of workbook use will be measured through 19 questions on implementation, intervention, and downstream costs of completing the workbook exercises.

One-sample Wilcoxon signed rank tests will be used to compare

average acceptability, self-efficacy, knowledge, and perceived knowledge levels to the comparison threshold levels to understand feasibility of the workbook.

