### 1.3. Purpose and Rationale

The objective of this project is to test the feasibility and implementation of our intervention, an educational workbook on the importance of cascade screening for Lynch Syndrome families. Fifteen patients diagnosed with Lynch Syndrome will test the workbook. We will assess the success of the workbook as a tool to improve cascade screening through post-intervention surveys and a qualitative interview. This feasibility study will provide foundational knowledge on the usefulness and acceptability of the workbook to inform an R01 to test if the intervention can improve cascade screening uptake when

used in the clinical environment.

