#### 4.2. Study Recruitment and Activities

The recruitment goal for genetic counselors is up to 5 genetic counselors. The recruitment goal for patients with Lynch Syndrome is 15 total patients between OSU, UNC, and LSI. There is no minimum or maximum number of patients that can be enrolled at each site up to the goal of 15 patients total.

At OSU and UNC, the co-PI or another member of the research team will contact genetic counselors who work with Lynch Syndrome patients via email and notify them of the study opportunity and provide an information sheet. Interested genetic counselors will use the workbook with their Lynch Syndrome patients as a support tool for their standard cascade screening. The genetic counselors will provide the workbook to patients likely to test positive for Lynch syndrome or patients who have already been confirmed to have Lynch syndrome. If the patient is positive for Lynch syndrome, during a counseling call/appointment, the genetic counselor will complete the first prompt of the workbook to identify family members with the patient and explain the other sections of the workbook. Patients will complete the other sections of the work independently. The genetic counselor will notify the patient that the workbook creators are interested in hearing feedback on the workbook use and if the patient is interested, the genetic counselor will send the name, phone number, and email address of the patient to the UNC research team via secure email.

Through the LSI Facebook page, the study team will post an advertisement for patients recently diagnosed with Lynch Syndrome. Interested patients will reach out to the UNC research team by emailing the address posted in the study advertisement.

[figure not shown]
For all patients referred by a genetic counselor or self-referred, the UNC research team will schedule and complete a study enrollment call to answer questions, confirm eligibility, and document informed consent to participate in a follow up interview and survey. For patients directed to the study from the LSI Facebook page advertisement, the UNC research team will provide the workbook following the enrollment call and the participant will complete the activities in the workbook independently.

The UNC research team will complete the follow up interview and survey with patients approximately 4 weeks after they received the workbook from their genetic counselor.

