## 9. APPENDICES

### 9.1. Patient Qualitative Semi-Structured Interview Guide

Theme #1: Practicality

Focus A: Understand Let's Talk complexity

Interview Questions:

1. Now that you have used the workbook, what did you think about it?
  - a. What did you like?
  - b. What did you dislike?
2. How complex or easy did you find it was to use "Let's Talk"?
3. How long did it take you to complete the exercises in the workbook?
  - a. For patients recruited through LSI: The first prompt covered identifying your first-degree relatives. How did identifying your relatives go? Could anything have improved the process of identifying relatives to contact?

4. How did you feel about the length of the workbook? (too long, too short, just right?)
5. Did you seek help from anyone when you used the workbook?
6. Was the organization of the exercises logical?
  - a. Would you change the order of the workbook sections?
7. Was there any part of the workbook you found difficult to understand or complete? Please explain.

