#### Theme #2: Demand

##### Focus A: Understand Let's Talk value to patients

Introduction: I'm also interested in hearing about how the workbook was valuable to you, if it was, and how it impacted the process of communicating with your family members.

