**Measure #3: Number of Relatives Who Sought Genetic Testing**

Question: Of the relatives you contacted, how many have sought genetic testing?

Conclusion: Is there anything else you'd like to share before we wrap up today?

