#### 9.5. Patient Workbook Costs Electronic Survey Segment

We are interested in understanding what time and resources are necessary to use the workbook. The next set of questions are intended to evaluate the time and resources needed to use this workbook starting from the genetic counseling appointment when you first received the workbook.

(1) Your genetic counseling appointment took place virtually. Did you have to purchase any new tools or resources to access your appointment? If yes, please describe.

(2) How far away do you live from your genetic counselor's physical office? Please estimate the distance in miles and the time it would have taken you to travel to and from your genetic counselor's physical office.

(3) How long did you use the workbook with your genetic counselor? (Please round your answer to the nearest 15 minutes.)

(4) Did you have to take time off work to talk with your genetic counselor?

(5) How many hours, if any, did you take off work to meet with your genetic counselor to learn about the workbook?

(6) After your genetic counseling appointment, how long did it take you to go through the workbook exercises? (Please round your answer to the nearest 15 minutes.)

(7) Did you take any time off work to use the workbook?

(8) How many hours, if any, did you take off work to use the workbook?

(9) Did you use the workbook in a virtual format (e.g. using a computer, tablet or phone) or did you print the workbook and fill it out by hand?

(10) Which pages of the workbook did you print? Please describe (e.g. all pages, pages 1-5, etc.)

- (11) After using the workbook, did you spend any additional time using other resources for Lynch Syndrome that were mentioned in the workbook?
- (12) How long did you spend using the extra resources mentioned in the workbook? (Please round your answer to the nearest 15 minutes.)
- (13) How many first-degree relatives did you communicate with after using the workbook?
- (14) Did you take any time off work to communicate with your relatives?
- (15) How many hours, if any, did you take off work to communicate with your relatives?
- (16) For each relative that you contacted, please list (1) how you communicated with them and (2) how long the entire communication process took from initial contact to follow up. Please consider time spent planning, communicating, and following up with relatives.

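### Integration is one of four themes to be coded in the transcripts, but the interview guide has no section or dedicated question on it

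*Combined protocol and SAP*

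**What the plan says.** Section 4.7.2 sets out a template analysis of the transcribed interviews, double coded in NVivo, and names the starting themes: "Expected themes (practicality, integration, demand, and reach) will be a prior coded in the transcripts". It adds that themes may be modified, dropped or supplemented as the codebook develops.

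The only interview guide is 9.1. Its first section is "Theme #1: Practicality", its second is "Theme #2: Demand", and its third covers reach. It then ends with "Conclusion: Is there anything else you'd like to share before we wrap up today".

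Two other statements show why fit with care is relevant. Section 4.2 has counselors at the clinical sites "use the workbook with their Lynch Syndrome patients as a support tool for their standard cascade screening". Section 1.3 says the results are meant "to inform an R01 to test if the intervention can improve cascade screening uptake when" the workbook is used in clinical practice. Section 2.1 frames the primary question as feasibility for health professionals.

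**The concern.** The guide is organised by the same theme names as the analysis plan, but one of the four names is missing. If the study runs as written, coders will look for integration in transcripts of interviews that never raised it.

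What is at stake is interpretation. If few or no remarks on integration appear, the analyst cannot tell whether patients saw no difficulty, had no experience of using the workbook alongside counselling, or were simply not asked. The follow-on trial would test the workbook in the clinic, so its designers will want to know how it sits beside counselling that patients already receive. This study names that topic in its analysis plan but does not plan to ask about it.

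**Working it through.** The plan gives no figure on this point, so the check sets the themes in 4.7.2 against every heading and question in 9.1, and then against the other instruments.

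**Interview guide (9.1)**

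| Theme in 4.7.2 | Section in 9.1 | Items |
|---|---|---|
| Practicality | Theme 1, Focus A and B | 7 + 4 = 11 numbered questions |
| Demand | Theme 2 | 3 numbered questions |
| Reach | Theme 3 | 4 measures (1, 2A, 2B, 3) |
| Integration | none | 0 |

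The themes run consecutively from 1 to 3 and the appendices from 9.1 to 9.5, so nothing suggests that an integration section was lost from the text.

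**Nearest interview questions**

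- Under practicality: "Did you seek help from anyone when you used the workbook". This asks about assistance, not about how the workbook fitted with counselling.
- Also under practicality, a sub-question for patients recruited through the advocacy group asks how identifying relatives went. It concerns one exercise.
- Focus B asks what extra materials would improve use. That is hypothetical and does not ask what care or materials the patient actually had.

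**Surveys (9.2 to 9.5)**

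- Sections 9.2 to 9.4 cover acceptability, self-efficacy, knowledge and perceived knowledge. None asks about fit with care.
- Items 1 to 5 of 9.5 concern the counselling appointment: tools bought, distance, time using the workbook with the counselor, and time off work. Item 6 separates out the time spent on the exercises afterwards. These are cost data, and they are not part of the transcripts that 4.7.2 codes.
- Item 11 of 9.5 asks "did you spend any additional time using other resources for Lynch Syndrome that were mentioned in the workbook". This too is a question about time, within a cost segment.

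**Provider side**

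Section 4.7.1 expects general feedback from providers. However, all five appendices are patient instruments, and 4.6, 4.7.2 and the events table in section 5 describe only patient interviews and surveys. Integration is therefore not picked up from counselors either.

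**Result**

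Three of the four named themes have dedicated questions. Integration has none in the guide, and no other instrument measures it.

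**The case against.** The strongest reply is that template analysis codes content, not guide headings. The interview is semi-structured, and several open questions could bring out remarks on integration: what the patient thought of the workbook, whom they asked for help, its good and bad effects, and the closing invitation. Section 4.7.2 also allows a theme to be removed. This stands in part. It is why the point is the lack of a dedicated question, and a reader who inferred that no data at all could arise would go too far. But unprompted remarks will vary by patient, and silence will stay ambiguous. Removing a theme because nobody was asked about it reflects the instrument, and should be reported as such.

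A second reply is that the documents never define integration. It could mean fit within the counselor's workflow, left over from a time when counselors had a larger role; the version 7.0 change log says references to them were removed. That origin is an inference, but the reading is plausible, and patient questions alone would not cover it. It does not remove the mismatch, because no provider instrument exists. It does mean that a definition has to come before any new question.

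Three stronger readings are tempting but not supported:

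- A reader might infer that counselling goes entirely unasked because item 11 of 9.5 is limited to resources named in the workbook. Items 1 to 5 do ask about the counselling appointment, although only as time and cost. The mismatch can be resolved without touching item 11.
- A reader might turn one theme in four into a quarter of the information lost. The count is of labels and says nothing about how much information each theme carries.
- A reader might infer that the saturation argument for 15 patients fails. Section 4.7.1 makes that argument for workbook feasibility among patients overall, not theme by theme.

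**Conclusion.** The point holds as a mismatch between the analysis plan and the instrument. One of the four themes named in 4.7.2 has no section and no dedicated question in 9.1, and neither the surveys nor a provider instrument fills the gap. As written, integration would be reported from chance remarks or not at all, and its absence could not be taken as evidence either way.

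The size is modest. No survey threshold, Wilcoxon test or sample-size figure depends on this theme, and the other three themes are unaffected. It is still worth correcting, because the theme bears on the primary question in 2.1 and on the purpose stated in 1.3.

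Two assumptions apply. First, integration is taken to mean fit with counselling or usual care, which suits 1.3, 2.1 and 4.2 but is not stated; under any other meaning the guide still has no section for it. Second, whether interviews remain to be done is unknown. The change log describes recruitment in the past tense, but the documents do not say that interviewing has finished.

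**What to change.** First, define integration in 4.7.2 in a sentence that says whether it concerns the patient's experience of care, the counselor's workflow, or both. Double coders need that definition in any case.

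Then take one of two routes.

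- **Interviews remain.** Add a short integration section to 9.1. For example: what counselling or other Lynch Syndrome materials did the patient receive before or while using the workbook; did the workbook add to, repeat or conflict with them; and at what point in care would it have been most useful? The wording works for patients from a clinic and from the advocacy group. Report how many patients were asked. If the definition includes counselor workflow, state that these questions do not assess it.
- **Interviews are complete.** Remove integration from the expected themes and state in the report that it was not assessed. Any remarks that arose unprompted can be described as such.

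The first route costs a few extra minutes per interview and a small amendment. The second costs the definition or deletion in 4.7.2 and a stated limitation.

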## 1. BACKGROUND AND RATIONALE

### 1.1. Study Synopsis

We will trial an educational workbook on family cascade screening for individuals diagnosed with Lynch Syndrome, a genetic predisposition for certain types of cancer. Up to 5 genetic counselors at Ohio State University (OSU) and the University of North Carolina at Chapel Hill (UNC Chapel Hill) as well as 15 patients at OSU, University of North Carolina at Chapel Hill (UNC Chapel Hill), and Lynch Syndrome International (LSI) will pilot test the workbook and we will conduct surveys and qualitative interviews to understand the feasibility, acceptability, practicality, and economic impact of the workbook. The research team developed the workbook in a previous project using implementation science strategies to identify and develop an intervention for barrier and facilitators to family screening for Lynch Syndrome.

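### The cost survey can describe patients' own time and resources, but not the economic impact and implementation cost announced in 1.1 and 4.7.2

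*Combined protocol and SAP*

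**What the plan says.** Section 1.1 says surveys and interviews will be used to "understand the feasibility, acceptability, practicality, and economic impact of the workbook". Section 4.7.2 describes the cost measure: "The cost of workbook use will be measured through 19 questions on implementation, intervention, and downstream costs of completing the workbook exercises". The primary question in 2.1 is whether the workbook is feasible for health professionals to use.

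Section 4.2 describes two delivery routes. At OSU and UNC the counselor hands over the workbook, works through the first prompt with the patient, explains the remaining sections and refers interested patients to the research team. For LSI patients the research team supplies the workbook after the enrollment call and the patient works alone.

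On time, 4.4 says "We expect genetic counselor participants to spend approximately 4 to 20 hours engaged in study activities over the approximately 9 months of enrollment" and, for patients, "We expect patient participants to spend approximately 8 hours engaged in study activities". It adds that counselor time depends on how many patients the counselor has enrolled.

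The 19 cost items are in 9.5, a patient survey. Item 3 asks "How long did you use the workbook with your genetic counselor", to the nearest 15 minutes. All the instruments in 9.1 to 9.5 are for patients. No counselor survey or time log appears, although 4.7.1 expects general feedback from providers.

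**The concern.** The scope of the claim and the scope of the data differ. Implementation cost is ordinarily borne at least partly by whoever delivers an intervention, and economic impact is wider still. The survey measures one party's burden. If its results are reported under the wording of 1.1 and 4.7.2, a patient-side figure will be read as the cost of implementing the workbook. For delivery through counselors that figure is too low by an unknown amount. This matters because 2.1 asks about use by health professionals, for whom delivery time is an obvious cost.

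A second gap concerns the LSI route. The introduction to 9.5 counts costs from the counseling appointment at which the workbook was received. LSI patients had no such appointment within the study. The interview guide (9.1) has an LSI-specific prompt; the cost survey has none.

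**Working it through.** **Step 1: whose cost each item measures.** The 19 items in 9.5 group as follows:

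- Items 1–5: the counseling appointment (equipment, distance, shared time, time off work).
- Items 6–12: working through the workbook, printing, extra resources.
- Items 13–18: contact with relatives.
- Item 19: unexpected costs to the patient.

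That is 5 + 7 + 6 + 1 = 19. Only item 3 carries provider time, and only the part shared with the patient, recalled at a follow-up about 4 weeks after receipt (4.2). Counselor preparation, referral and later follow-up have no item. Neither does the research team's provision of the workbook to LSI patients.

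**Step 2: can the gap be sized?** The plan gives no provider share, so there is no figure to reproduce. The inputs are:

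- Patients: "The recruitment goal for patients with Lynch Syndrome is 15 total patients between OSU, UNC, and LSI" (4.2).
- Counselors: "The recruitment goal for genetic counselors is up to 5 genetic counselors" (4.2), so G runs from 0 to 5.
- Hours (4.4): 8 per patient, h = 4 to 20 per counselor.

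Patient total: 15 × 8 = 120 h. Counselor share of person-time = G·h / (G·h + 120).

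| Counselors G | h = 4 | h = 20 |
|---|---|---|
| 0 | 0% | 0% |
| 1 | 4/124 = 3.2% | 20/140 = 14.3% |
| 3 | 12/132 = 9.1% | 60/180 = 33.3% |
| 5 | 20/140 = 14.3% | 100/220 = 45.5% |

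With five counselors and all 15 patients on their route, counselor time per patient is 20/15 = 1.33 h to 100/15 = 6.67 h.

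**Step 3: effect of the LSI route.** Assume that counselor hours scale with the number k of counselor-route patients, from 20 to 100 h in total when k = 15. The share is then (20k/15)/(20k/15 + 120) to (100k/15)/(100k/15 + 120):

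- k = 0: 0%.
- k = 5: 6.67/126.67 = 5.3% to 33.3/153.3 = 21.7%.
- k = 10: 13.3/133.3 = 10.0% to 66.7/186.7 = 35.7%.
- k = 15: 14.3% to 45.5%.

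**Step 4: what item 3 recovers.** The plan gives no session length. Assuming 15 to 60 minutes, joint time is 0.25/8.25 = 3.0% to 1/9 = 11.1% of combined person-time for one patient (counselor session time plus 8 patient hours). Against 1.33 to 6.67 counselor hours per patient it recovers between 0.25/6.67 = about 4% and 1/1.33 = 75%. Item 3 could therefore capture almost none or most of the counselor input.

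**Step 5: limits of these figures.** Section 4.4 labels both sets of hours as study activities and does not separate workbook delivery from research tasks. Patient hours may include the enrollment call, interview and survey; counselor hours may include the study introduction. Sections 4.1 and 4.4 also disagree on individual patient participation (about 1 versus 3 months) and counselor participation (about 24 versus 9 months), so the 4.4 time estimates are themselves unsettled.

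**The case against.** The best defence is that the plan never promised a provider perspective. The sentence in 4.7.2 refers to the costs of completing the exercises, and 9.5 is labelled as patient costs. The three categories can be matched to the patient's side: appointment, workbook use, contact with relatives. Section 2 sets no economic objective and says there are no secondary objectives. Cost has no threshold, test, unit cost or planned total. On this reading the survey does what it was built for.

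Much of that stands. It makes this a matter of scope and labelling and leaves the primary analysis untouched. It does not remove the point: 1.1 states the economic aim without limiting it to patients, 4.7.2 claims implementation costs without naming a perspective, and 2.1 is framed around health professionals. The absence of unit costs and a planned total also makes an economic-impact claim harder to support.

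Two stronger readings are tempting, and the documents support neither. A reader might infer that provider time is left out altogether. It is not, because item 3 records shared counselor time by patient report. A reader might also infer that 14% to 45% of the workbook's cost is missing. Those percentages are shares of undivided study hours, not of cost. They hold only with all five counselors and no LSI patients, and item 3 already recovers part of the time. Nor is 14% a floor, since the plan sets no minimum number of counselors.

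**Conclusion.** The point holds as a mismatch between claim and data. The survey can support a description of patient-incurred time and resource use. It cannot support implementation cost or economic impact as 1.1 and 4.7.2 word them.

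The size of the omission cannot be computed from the documents. Section 4.4 bounds counselor hours at 0% to about 45% of combined person-time. The position within that range depends on how many counselors take part, how many patients come through LSI, and how much of the stated time is workbook delivery. The 0% case means only that no patient came through a counselor. It does not show that delivery by health professionals is free; the study would then have nothing to say about it.

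A reader might infer that an underestimated cost would pass into the planned R01. The documents do not say so: 1.3 says this study informs that application on usefulness and acceptability, and nowhere is a cost estimate said to be carried forward.

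This should be corrected, but it does not threaten the trial.

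**What to change.** 1. In 1.1 and 4.7.2, replace the economic-impact and implementation-cost wording with patient-incurred time and resource use, and state that provider implementation cost is not estimated. This can be done even if recruitment is over.

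2. If any counselor-route patients are still to be enrolled, add one REDCap field at referral for counselor minutes on workbook preparation and delivery, and report it beside patient time. Under 4.2 the counselor already emails the research team at that point. Later counselor follow-up would remain uncollected, and the report should say so. The field may capture little: the summary of changes says LSI recruitment was prioritized, and the documents do not say how many counselor-route patients there are.

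3. Report LSI patients separately, labelled as having no counselor input, with research-team provision not costed. Calling this route free of provider input would be wrong, because the research team supplies the workbook. Do not apply to them the 9.5 items that presuppose an appointment at which the workbook was received. That covers items 1 to 5. Item 6 needs only its opening clause removed, because it also measures time spent on the exercises. For surveys already completed, treat items 1 to 5 as not applicable for LSI patients.

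The cost is a narrower claim, wording changes in two sections, small survey edits and about a minute of counselor time per referred patient.
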